#### **4.1.3 Maximum Tolerated Dose**

The Maximum Tolerated Dose (MTD) is defined as the prior dose level below the drug-combination that causes DLT, in at least 2 patients in a cohort of at least 6 patients.

If, at any dose level, a patient fails to complete cycle 1 for reasons other than DLT, that patient is deemed unevaluable for determining the MTD and may be replaced. Such a patient will be included in the evaluation of toxicity and efficacy.

[figure not shown]
Exploration of different combination dosing regimens may be investigated to provide a tolerated dose of AZD2281 combined with cisplatin which can be investigated in further studies, however the highest dose to be explored will be 400 mg bid. (The MTD established in the monotherapy Phase I study).

**Figure 2** Study flow chart - Continuous dosing schedule

\* PK blood draws will not be performed for patients enrolled into an intermittent dosing cohort

**Figure 3** Study flow chart - Intermittent dosing schedule

Note: Patients can continue treatment for as long as they are benefiting and are free from significant toxicity. After patients complete 6 cycles of cisplatin based therapy, cisplatin may be discontinued and AZD2281 alone may be continued at the optimal monotherapy dose (i.e. 400 mg bid) at the investigators discretion. See Section 4.2.3 and Table 5 for full details.

## **4.2 Schedule of assessments, investigations and sampling**

### **4.2.1 Baseline (Screening assessments)**

The following assessments and procedures should be performed within 21 days prior to first dose of study treatment. A cycle of treatment is scheduled to last 3 weeks (21 days). For details of the schedule and nature of the assessments, see below

- Signed informed consent
- Date of birth and race
- BRCA1/2 mutation status, if known from previous testing (not required for enrolment)
- Menopausal status; serum or urine pregnancy test for women of childbearing potential (preferably within 7 days prior to treatment start)
- Medical and surgical history
- Current and concomitant medications including previous cancer therapies (if applicable)
- Physical examination; ECOG performance status, vital signs (blood pressure and pulse rate, body temperature), 12-lead ECG, height and body weight
- Haematology, clinical chemistry and urinalysis
- Tumour assessment:
  - Chest/abdomen Pelvis CT or MRI & other regions as clinically indicated
- Adverse events must be captured from time of consent

### **4.2.2 On trial assessments**

The first cycle of cisplatin treatment will be administered once the patient has been confirmed as being eligible for inclusion into the study. Treatment cycles of cisplatin will have duration of 21 days each. Patients will self administer AZD2281 at home except on the days when PK profiles will be taken. PK blood draws will not be performed for patients enrolled into an intermittent dosing cohort.

Patients will attend the clinic on a periodic basis and the following assessments will be performed at timepoints specified in the study schedule (see [Table 4](#))

- Physical examination including ECOG performance status (day 1 of each 21 day period) and vital signs every visit

- ECG
  - Baseline, at the end of each of the first two cycles of cisplatin, at the end of treatment and at the final follow-up and if clinically indicated at any other time
- Haematology, clinical chemistry
- Creatinine Clearance should be calculated every cycle based on serum creatinine
- Serum or urine pregnancy test for women of childbearing potential (prior to starting treatment). If the test is positive then a confirmatory test should be performed.
- PK samples for determination of plasma AZD2281 (visit 2 and 3)  
\*Excluding patients on intermittent dosing
- AE & concomitant medications (every visit)
- Tumour assessment
  - Chest/Abdomen Pelvis CT or MRI & other regions as clinically indicated
- An optional pharmacogenetic sample will be obtained from consenting patients and stored for long-term experimental pharmacogenetic analysis
- Blood samples for pharmacokinetic analysis (Continuous dosing only)

#### **4.2.3 AZD2281 Monotherapy**

Upon completion of cycle 6 (ie, 21 days after last dose of chemotherapy), cisplatin may be discontinued and AZD2281 alone may be continued at the optimal monotherapy dose (i.e. 400 mg bid) at the investigators discretion.

The first dose of olaparib maintenance (Day 1 of olaparib maintenance phase) is the day after the chemotherapy discontinuation visit.

Following the patients' first dose of olaparib maintenance, they will return to the clinic for safety assessments at days 8, 15, 22 and 43, and then every 6 weeks thereafter relative to monotherapy day1 until objective disease progression as per RECIST criteria (assessed every 12 weeks), unless any other discontinuation criteria are met. See [Table 5](#) for specific assessments and time points.

#### **4.2.4 Treatment discontinuation visit**

Patients should be discontinued from study treatment if any discontinuation criteria are fulfilled (see Section [4.4.6.1](#)). The assessments to be carried out at the visit are detailed in the study schedules ([Table 4](#), and [Table 5](#) for Monotherapy phase).

#### **4.2.5 Withdrawal visit**

Patients should be withdrawn from the study if discontinuation criteria are fulfilled (see Section 4.4.6.1). The assessments to be carried out at the visit are detailed in the study plans (Table 4 and Table 5 for Monotherapy phase).

#### **4.2.6 Final follow up visit**

A final follow-up visit should be conducted 30 days after the last dose of AZD2281. Any serious and/or non-serious AEs ongoing at the time of the Withdrawal Visit or which have occurred during the defined 30-day follow-up period must be followed-up (in accordance with Section 5.10.3). Appropriate safety evaluations should be repeated and/or additional tests performed at any time when clinically indicated, or at the discretion of the Investigator, until resolution, unless, in the Investigator's opinion, the condition is unlikely to resolve due to the patient's underlying disease. The patient may have the 30-day follow-up blood samples taken at a local institution as an alternative to the investigator site, if the patient is too sick to travel. If the patient is lost to follow-up, then this should be noted in the CRF. The assessments to be carried out at the 30 day follow up visit are detailed in the study schedule (Table 4 and Table 5 for the monotherapy phase)

**Table 4 Study plan (see Section 5 for further details)**

Cycle	0	0	1			2			3,4,5 hq			Withdrawal	30 Day follow up (+/-7days)
Visit Number	1	2*	3	4	5	6	7	8	9	10	11		
Week	-	1	2	3	4	5	6	7	8	9	10		
Study Day	Scr	1-4	8	15	22	29	36	43	50	57	64		
Informed Consent	X a												
Demography	X a												
Confirm eligibility	X c												
Medical / Surgical History	X a												
Physical Examination b	X c		X			X			X j			X	X
Audiometric testing	X j								X j			X j	
Vital signs d	X c		X	X	X	X	X	X	X	X	X	X	
Performance Status	X c		X			X			X d			X	
ECG e	X c				X			X				X	X
Pregnancy test f	X		X										
Tumour assessment p	X								X			X	
Haematology g	X c		X	X	X	X	X	X	X	X	X	X	X
Clinical Chemistry g	X c		X	X	X	X	X	X	X	X	X	X	X
Urinalysis g	X c		X	X	X	X	X	X	X	X	X	X	X
PGx blood sample		X l											
PK blood sampling AZD2281		X i	X i										
Cisplatin infusion			X			X			X h				

**Table 4 Study plan (see Section 5 for further details)**

AZD2281 dosing		X k	X mn	← dependent on cohort → continuous or intermittent bid dosing									
Adverse Events and con meds o	X	X	X	X	X	X	X	X	X	X	X	X	X

- \* Visit 2 is not applicable for patients enrolled in the intermittent dosing cohort, (PK is not required and therefore the single dose of AZD2281 is not applicable) – assessments that are scheduled for this visit can be done at visit 3 (Day 1 dosing with cisplatin)
- a To be performed within 21 days of planned day –1
- b Physical examination including weight and height for determination of cisplatin dose (height screening only)
- c To be performed within 7 days before study day -1. Eligibility to be confirmed before commencing treatment on study day 1
- d Vital signs to include blood pressure (BP), pulse rate (PR) and body temperature. BP and PR should be taken after the patient has been sitting at rest for 5 minutes and before blood sampling. At the PIs discretion and if the patient has completed 4 cycles of combination therapy, vital signs, performance status, haematology, and clinical chemistry assessments may be performed at the beginning of each cycle and not at each weekly visit, unless clinically indicated.
- e ECG to be performed at baseline, at the end of each of the first 2 cycles of cisplatin, at the end of treatment and at final follow up and if clinically indicated at any other time
- f Two pregnancy tests on blood or urine samples will be performed for pre-menopausal women of childbearing potential one within 28 days prior to starting treatment and the other on Day 1 of the study prior to commencing treatment. If results are positive the patient is ineligible/must be discontinued from the study. In the event of a suspected pregnancy during the study, the test should be repeated.
- g Haematology, clinical chemistry and urinalysis to be performed weekly +/- 1 day. Samples only need to be collected predose on day 1 if the screening assessments were performed more than 3 days before to day 1. At the PIs discretion and if the patient has completed 4 cycles of combination therapy, vital signs, haematology, and clinical chemistry assessments may be performed at the beginning of each cycle and not at each weekly visit, unless clinically indicated.
- h Patients receiving benefit from treatment with AZD2281 and cisplatin can continue provided they are receiving benefit and are free from intolerated toxicity. Routine safety visits will be performed until discontinuation. Tumour assessments will be performed at the end of every 2 cycles of cisplatin (6 weekly intervals). In the event that cisplatin is permanently discontinued, treatment with AZD2281 alone may continue. If cisplatin is permanently discontinued, patients should have weekly visits for the first two months (8 weeks) of AZD2281 monotherapy, and then every month (4 weeks) after 2 months of AZD2281 monotherapy. After the patients completes 4 cycles of cisplatin at the full dose of 75 mg/m^2, subsequent cycles of cisplatin may be administered at a reduced dose as low as and including 50 mg/m^2 at the investigator's discretion. After patients complete 6 cycles of cisplatin based therapy, cisplatin may be discontinued and AZD2281 alone may be continued at the optimal monotherapy dose (i.e. 400 mg bid) at the investigators discretion. See Section 4.5.2.2 for full details. Note: After protocol amendment 6 is approved, patients on AZD2281 monotherapy can have their visit schedule modified as per Table 5 and Section 4.2.3.
- i Blood samples for AZD2281 PK will be taken relative to the morning dose of AZD2281: predose, 1,2,3,4,6, 8, 12 hrs post dose. A 10 minute time window (+/- 10 minutes) will be allowed but the samples should be taken as close to the nominal time point as possible. If it is not possible to take the 12 hour sample at the correct time, take the sample as close to 12 hours as possible ensuring this sample is taken at the same time at Visit 2 and Visit 3. PK blood draws will not be performed for patients enrolled into an intermittent dosing cohorts.

- j Audiometric testing should be performed at baseline, at the end of the 2nd, 4th and 6th cycles of cisplatin and as clinically indicated thereafter. A final audiogram should be done at study completion. In the event that cisplatin is permanently discontinued, only the final audiometric test done at study completion is required, unless otherwise clinically indicated.
- k At visit 2, a single dose of AZD2281 (dose dependent on the cohort) will be given in conjunction with collection of PK samples (see footnote 'i' above). The medication bottle will have been labelled with the patient's E Code and be retained by the study site until the patient returns for Visit 3, when the same bottle will be dispensed to the patient. Note: the single dose is only applicable for patients enrolled in a continuous dosing cohort.
- l Blood sample for PGx (optional), patients enrolled on an intermittent dosing cohort can have this blood sample taken at visit 3
- m AZD2281 will be dispensed for twice daily dosing either on a continuous or intermittent basis. Instruct patients to return both used and unused study drug bottles and study drug at their next scheduled study visit.
- n Throughout the duration of the study, dispense sufficient number of bottles for an appropriate number of days/cycles of treatment depending on the dose level. Used and unused study AZD2281 should be accounted for and compliance checked (including a review of the patient diary card)
- o Adverse events must be collected from the time of informed consent, throughout the treatment period and up to and including the 30-day post-study follow-up period. All ongoing, AEs at discontinuation must be monitored until resolution unless, in the Investigator's opinion, the condition is unlikely to resolve due to the patient's underlying disease. After discontinuation from treatment, patients must be followed up for all existing and new AEs for 30 calendar days (if SAEs, they must be reported to AstraZeneca within 24 hours) and followed until resolution unless, in the opinion of the Investigator, the condition is unlikely to resolve due to the patient's underlying disease. All relevant concomitant medications including those stopped within 6 weeks of first dose AZD2281, should be recorded on the CRF. Con-meds should be recorded up until the 30 day follow up visit ensuring all medication stop dates have been entered where applicable.
- p RECIST assessment by CT or MRI scans of chest abdomen, pelvis and other regions including chest as clinically indicated for the assessment of disease. Baseline assessment may be performed up to 28 days prior to study day 1 (see [Appendix D](#)). Follow up assessments performed at the end of every 2 cycles of treatment +/- 1 week (see [Appendix D](#)). Confirmation of response will be at the next scheduled assessment. Once a patient has completed 3 months (12 weeks) of monotherapy, tumour assessments are only required at the end of every 3 months (every 12 weeks (+/- 1 week)). At withdrawal, RECIST assessment is required, however if the previous RECIST assessment was performed within 6 weeks of withdrawal, the withdrawal RECIST assessment should be performed but can be missed at the discretion of the investigator.
- q Until a patient is withdrawn from the treatment or the study the assessments should be carried out as in visits 9/10/11

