### 4.1 Overall study design

The study is a Phase I non-randomised, open label, dose finding study, to determine the maximum tolerated dose of AZD2281 that can be combined with cisplatin in patients with advanced solid tumours.

Each cohort will comprise a minimum of 3 evaluable patients. If 1 patient from the initial 3 experiences DLT the cohort will be expanded to at least 6 patients. It is expected that 60 patients will be enrolled.

Once the desired dose or MTD of the combination therapy has been determined (or the highest dose level has been explored) the cohort will be expanded to ensure that there are 6 evaluable patients who have completed four cycles of treatment.

If continuous dosing is not tolerated, intermittent dosing will be explored. An intermittent dosing cohort will be opened to enrol 12 patients at the following dose:

- AZD2281 at 100 mg bid for days 1-10 of a 21 day cycle with 75 mg/m^2 of cisplatin on day 1 of a 21 day cycle
- Day 1 of cisplatin and day 1 of AZD2281 are the same day

In the event that the first intermittent dose cohort is not tolerated, further cohorts may be investigated with a starting dose of AZD2281 at 50 mg bid for days 1-5 of a 21 day cycle with 75 mg/m^2 of cisplatin.

Further cohorts may be considered following review by the safety monitoring committee. The cohort options to be considered are described in [Table 3](#).

For the continuous dosing regimens, at visit 2, study day 1 (+3 days), only a morning dose of AZD2281 will be administered. On the morning of study day 1, patients will attend the clinic to begin cycle 0 where, in addition to receiving a cohort-specific oral dose of AZD2281, samples for a full 12-hour plasma PK profile will be taken. From Cycle 1 at visit 3 Study day

8 and on each day thereafter, AZD2281 will be taken orally twice-daily. Also on day 8, cisplatin will be administered 2 hours after AZD2281 administration. This will be day 1 of the 21-day cycle. A full 12-hour plasma PK profile will also be repeated at this visit to enable a comparison of AZD2281 PK when given alone and in combination with cisplatin. Pharmacokinetic (PK) blood samples will be collected for patients receiving continuous dosing of AZD2281 as described in Section 5.3.

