## **4.3 Rationale and risk/benefit assessment**

### **4.3.1 Rationale for study design, doses and control groups**

This is a Phase I non-randomised, open label, dose finding study, to determine the maximum tolerated dose of AZD2281 that can be combined with cisplatin in patients with advanced solid tumours.

This study is designed to provide safety and tolerability data for AZD2281 in combination with cisplatin and PK data for AZD2281 alone and in combination with cisplatin.

For the continuous dosing combination treatment regimen, patients will attend the clinic 1 week (4-7 days) before the combination treatment is due and a single dose of AZD2281 will be given (dose depending on cohort recruited into). Plasma PK samples will be obtained over 12 hours. A PK profile will be again taken on day 1 of cycle 1 of cisplatin (day 8) when AZD2281 will be given in the presence of cisplatin. This will permit a comparison of the exposure to AZD2281 when given with cisplatin and without. Patients will be closely monitored for safety and dose levels will be assessed once at least 3 evaluable patients have completed 21 days of combination treatment or have experienced a DLT.

For intermittent dosing cohorts, no PK is required; therefore patients are only required to start their AZD2281 dosing on the same day as cisplatin is administered, unless a different dose schedule is advised by the safety monitoring committee.

The dose levels of 50, 100, 200 and 400 mg (twice-daily) either continuous or intermittent have been chosen, as previous Phase I studies have demonstrated that they are all generally well tolerated, yield systemic concentrations of AZD2281 and are likely to be biologically active.

The Phase I study design takes into account patient population, the emerging toxicity profile of AZD2281, pharmacology of cisplatin and potential for interactions that might impart treatment related toxicities. There is little evidence to suggest that there will be an ADME based interaction when the two drugs are administered in combination.

The number of patients is based on the desire to gain adequate information whilst exposing as few patients as possible to the study medication and procedures.

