## **5.6.2 Other Safety Assessments**

### **5.6.2.1 Serum or urine pregnancy test**

Two pregnancy tests on blood or urine samples will be performed for pre-menopausal women of childbearing potential one within 28 days prior to the start of study treatment and the other on Day 1 of the study prior to commencing treatment. Tests will be performed by the hospital's local laboratory. If results are positive the patient is ineligible/must be discontinued

from the study. In the event of a suspected pregnancy during the study, the test should be repeated.

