## 1. INSTRUCTIONS FOR HANDLING PHARMACOKINETIC SAMPLES

### 1.1 Collection and handling of pharmacokinetic blood samples

A full 12 hour PK profile for the determination of AZD2281 plasma concentration will be collected at the following time points:

Study day	Time point
1	Predose, 1, 2, 3, 4, 6, 8 and 12 hrs post AZD2281 dose*
2	*
3	*
4	*
5	
6	
7	
8	Predose, 1, 2, 3, 4, 6, 8 and 12 hrs post AZD2281 dose
9	

\* Single dose monotherapy profile can be taken on any day between 1-4

PK blood draws will not be performed for patients enrolled into an intermittent dosing cohort.

Venous blood samples (4 mL) will be collected into pre-labelled tubes containing LITHIUM HEPARIN anticoagulant at the times shown in the study plan and thoroughly mixed. Pharmacokinetic sample tubes will be clearly labelled with the compound name, protocol number, subject enrolment code (or centre and patient number), study day, date of sample collection and nominal time-point. The date and time of sample collection will be recorded on CRFs.

Venous blood samples taken into LITHIUM HEPARIN anticoagulant will be centrifuged at 2000G for 10 minutes at room temperature within 30 minutes of collection, to provide plasma for analysis of AZD2281. Following centrifugation, each plasma sample should be transferred to a separate individually labelled cryo vial and stored at  $-20^{\circ}\text{C}$  within 1 hour of blood collection. Plasma samples should be stored at  $-20^{\circ}\text{C}$  or below at all times until analysis.

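### In continuous cohorts, Table 4 marks the second pregnancy test 4–7 days after the first AZD2281 dose, contradicting its own footnote f and section 5.6.2.1

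*Protocol*

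**What the plan says.** Section 5.6.2.1 of the Protocol sets two tests: "one within 28 days prior to the start of study treatment and the other on Day 1 of the study prior to commencing treatment". Footnote f to Table 4 gives the same rule, with the second test "the other on Day 1 of the study prior to commencing treatment". Section 4.2.2 likewise places the test before treatment starts.

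For the continuous regimens, section 4.1 states that "at visit 2, study day 1 (+3 days), only a morning dose of AZD2281 will be administered". Footnote k to Table 4 agrees: "At visit 2, a single dose of AZD2281 (dose dependent on the cohort) will be given in conjunction with collection of PK samples". Appendix E (section 1.1) adds that the "Single dose monotherapy profile can be taken on any day between 1-4". Cisplatin comes a week later: "Also on day 8, cisplatin will be administered 2 hours after AZD2281 administration".

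The row of Table 4 labelled "Pregnancy test f" is marked at Visit 1 (screening) and Visit 3 (study day 8). The Visit 2 cell (study day 1–4) is empty.

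For the intermittent regimens, the asterisked note to Table 4 says that Visit 2 does not apply, so Visit 3 is the first dosing day.

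**The concern.** Table 4 is the visit-by-visit schedule that sites work from. For a continuous-cohort patient it shows an AZD2281 dose at Visit 2 and the second pregnancy test only at Visit 3. A test that the text requires before treatment is therefore scheduled after treatment has begun.

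The purpose of a Day 1 test is to cover the interval since screening. If it is done at Visit 3, a pregnancy arising or becoming detectable in that interval is exposed to one AZD2281 dose. Section 1.2.3 reports major foetal malformations in rats and says that no dose free of adverse foetal effects was established. Sites could also diverge, some following the footnote and others the grid mark.

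**Working it through.** No sample size, power or alpha is involved. The check sets the places side by side and takes one difference in days.

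1. **When is the second test due?** Footnote f and section 5.6.2.1: Day 1 of the study, before treatment.

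2. **When does treatment start in continuous cohorts?** Section 4.1, footnote k and Appendix E: at Visit 2, study day 1 with a window of +3 days, so study day 1 to 4. The study-day row of Table 4 shows the same range. Footnote c, on confirming eligibility, also ties the start of treatment to study day 1.

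3. **Where does the grid put the second test?** At Visit 3, study day 8.

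4. **Is the blank at Visit 2 genuine?** Neighbouring rows of the table keep their columns: the PGx sample is marked at Visit 2 only, PK sampling at Visits 2 and 3, and cisplatin first at Visit 3. The AZD2281 dosing row is marked at Visit 2. The blank is therefore not a shifted column.

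5. **Gap between first dose and gridded test** = study day of Visit 3 − study day of the single dose:
   - shortest: 8 − 4 = 4 days
   - longest: 8 − 1 = 7 days

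   This agrees with section 4.3.1: "patients will attend the clinic 1 week (4-7 days) before the combination treatment is due and a single dose of AZD2281 will be given".

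6. **Age of the only earlier test at the first dose:** up to 28 days under footnote f; up to 21 days, preferably 7, under section 4.2.1.

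7. **Exposure before the gridded test:** one morning dose of 50, 100 or 200 mg according to cohort, or 400 mg if that level is opened. If the Visit 3 test is done before dosing that day, it still precedes cisplatin and the repeated dosing of cycle 1 (21 days × 2 = 42 planned doses).

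8. **After the correction:** with the mark at Visit 2 before the dose, the test falls on the day of the first dose, 0 days before it instead of 4 to 7 days after it. In the intermittent cohorts the Visit 3 mark already satisfies the rule.

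**The case against.** The strongest reply is that the governing text is right. Footnote f is attached to the row itself, section 5.6.2.1 repeats the rule, section 4.2.2 agrees, and the table's title sends the reader to Section 5. A site would miss the pre-dose test only by acting on the bare mark and disregarding all of these. This stands, and it is the main reason the point is minor. It does not make the mark correct.

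A second reply is that Day 1 may mean the cisplatin day. The protocol uses the term loosely: the asterisked note calls Visit 3 Day 1 dosing with cisplatin, and footnote g speaks of day 1 pre-dose samples although the laboratory rows are blank at Visit 2. That probably explains the slip. It does not remove the conflict, because footnote f refers to Day 1 of the study and to the time before treatment begins, and section 4.1 places study day 1 at the Visit 2 dose.

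A reader might also infer more than the documents support:

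- **That women could be dosed with no pregnancy test.** They could not. Inclusion criterion 6 requires a negative test, exclusion criterion 7 excludes a positive one and requires two forms of contraception, and footnote c requires eligibility to be confirmed before treatment on study day 1.
- **That continuous cohorts need a third test.** Both footnote f and section 5.6.2.1 fix the number at two. A further test at Visit 3 would be a reasonable precaution, but nothing in the protocol calls for it.
- **That the grid is wrong for everyone.** It is right for the intermittent cohorts.

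**Conclusion.** The inconsistency is real but minor. For continuous cohorts the pregnancy row of Table 4 contradicts footnote f and section 5.6.2.1 by placing the second test 4 to 7 days after the first AZD2281 dose.

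The effect is confined to women of childbearing potential in those cohorts. Their number is not given and cannot be derived, because replacements, the MTD expansion and a possible 400 mg cohort can add to the cohorts in Table 2. What is at stake for each is one AZD2281 dose given on the screening test alone, with eligibility confirmation and contraception still in force. This assumes that a site follows the grid mark rather than the footnote. DLT counting, the MTD, PK and ORR do not change.

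It is worth correcting because the row schedules a safeguard against foetal exposure and the correction is almost free.

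**What to change.** In the pregnancy row of Table 4, make the second mark cohort-specific: at Visit 2, before the single AZD2281 dose, for continuous cohorts; at Visit 3, before dosing, for intermittent cohorts.

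The wording of footnote f and section 5.6.2.1 can stand. Adding the visit number for each type of cohort is optional but would help, since Visit 2 may fall on any of study days 1 to 4 and Day 1 is used in two senses.

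The cost is one moved mark and, if wanted, a short clarification in two places. The total remains two tests, and continuous-cohort patients already attend Visit 2. Retaining an extra test at Visit 3 for them is at the sponsor's discretion.
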